18	Bibliography	35

Preface

This document is aimed at giving authorities the rationale, objectives, design and proposed analysis, methodology, monitoring, conduct and record-keeping of a clinical investigation for ablative treatment of cutaneous neurofibromas (cNF) by a new ultrasound therapeutic methodology developed for targeted treatment of skin lesions called high intensity focused ultrasound (HIFU). The document is structured to follow the outline template for clinical investigation plans stated in Annex A of ISO14155:2020.

The study is conducted in parallel in two centers, one in Copenhagen, Denmark and one in Gothenburg, Sweden; each center having special explorative tasks e.g. lesional control by noninvasive imaging using 20 MHz ultrasound imaging assessment (Copenhagen) and by punch biopsy (Gothenburg).

An addition, specific assessment of the ethical aspects of the investigation is included in Appendix 1. This assessment follows and discusses specific issues required by the national ethical committees in the two countries where the centers are located. For Denmark ethical issues are governed and approved by "De videnskabsetiske medicinske komiteer (VMK)", while "Etikprövningsmyndigheten" governs ethical approvals in Sweden.

List of abbreviations and acronyms

NF1	—	Neurofibromatosis Type I
-----	---	--------------------------

- cNF Cutaneous Neurofibromas
- AE Adverse Event
- CIP Clinical Investigation Plan (according to ISO14155:2020).
- ClinRo Clinician Reported Outcomes
- CRF Case Report Form
- DK Denmark
- GCP Good Clinical Practice
- HIFU High Intensity Focused Ultrasound
- IB Investigators Brochure
- MDD European Council Directive 93/42/EEC of 14 June 1993 concerning medical devices
- MDR Regulation (EU) 2017/745 Regulation of the European Parliament on medical devices
- NFD Nominal Focal Depth
- OCT Optical Coherence Tomography
- PRO Patient Reported Outcome
- QoL Quality of Life
- SAE Serious Adverse Event
- SE Sweden
- US Ultrasound Scanning

1 Identification of CIP

Protocol ID	cNF-HIFU2101. CIV-21-09-037759
Study type	Multicenter (two-center) open-label study in humans (hospital outpatients)
Study device	TOOsonix System ONE-M A 20 MHz focused ultrasound device for controlled ablative treatment of cNF
Coordinating Clinical Investigator	[name] Chief Physician Ass. Professor, PhD, specialist in dermatology DK MD registration ID: [name] Department of dermatology, Bispebjerg University Hospital [name] Email: [contact]
Principal investigator Denmark	[name] Chief Physician Professor, dr. med., specialist in dermatology DK MD registration ID: [name] Department of dermatology, Bispebjerg University Hospital, [name] Email: [contact] [contact]
Principal investigator Sweden	[name] [name], PhD, specialist in dermatology SE MD registration ID: [name] Department of Dermatology and Venereology, Sahlgrenska University Hospital [name] Email: [contact] [contact]
Investigator Sweden	[name] Chief Physician PhD, Specialist in Dermatology Department of Dermatology and Venereology, Sahlgrenska University Hospital [name]
GCP support Denmark (pending contract)	GCP-enheden ved Københavns Universitetshospital Frederiksberg Hospital [name] E-mail:[contact] Tlf: [name]
GCP support Sweden (pending contract)	Gothia Forum for Clinical Studies Research Support Office Sahlgrenska University Hospital [name] Email: [contact] [contact]

Table 1. Planned activities in the clinical investigation. The investigation consists of a single treatment session (Visit 2) with 3 subsequent follow-up evaluations. The first data analysis and report on primary end-points will be done as an interim assessment after the 3-month visit has been completed by all participants (Visit 4). Primary and secondary end-points are concluded in a final report after all participants have completed the 9-month visit (Visit 5).

Visit number	1	2	3	4	5	6
Event Name	Pre-study	Day 0	7 ± 3 days	12 ± 2 weeks	24 ± 2 weeks	39 ± 3 weeks
			(1 week)	(3 months)	(6 months)	(9 months)
	Consent, Screening and Enrollment	Pre-treatment documentation, treatment, and post- treatment assessments	Evaluation of wound generation	Evaluation of healing and surveillance for any new lesions	Evaluation of healing and surveillance for any new lesions	Evaluation of healing and surveillance for any new lesions
Clinical evaluation	х	x	х	х	х	x
Inclusion and registration	х					
Informed consent	х					
Photo documentation 2D		X1	х	х	х	x
Photo documentation 3D		X1	х	х	х	x
Ultrasound Imaging Assessment (Bispebjerg Hospital)		X1	х	х	х	x
HIFU treatment		X2				
Participant questions and scoring		X1	х	х	х	x
Medical team questions and scoring		X1	х	х	х	x
Adverse Event Reporting		X1	х	х	х	x
Biopsy of 1-3 treated cNF ³ (Sahlgrenska Sjukhuset)			х	х		
Biopsy of 1 untreated cNF (Sahlgrenska Sjukhuset)			х			

1 = Data collection should occur immediately before treatment and again within one hour after treatment

2 = A minimum of 5 cNF 2-5 mm in size are required for enrollment. A minimum of 3 and a maxumum of 9 cNF will be treated and assessed across visits 2-6

3 = The minimum number of cNF to be biopsied is 3 (two treated and one control). The maximum number of cNF to be biopsied is 7. The biopsies will occur for cNF that are between 2-5 mm in size at visits 3 and 4. There will be one untreated cNF biopsied at visit 3. A minimum of one treated cNF will be biopsied at both visit 3 and visit 4.

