The hypothesis of this study is, that small and highly localized acoustic focal zones produced by a new HIFU device non-invasively can induce acute cell-death in cutaneous neurofibromas (cNF) without disrupting the skin's basement membrane. The healing of the treated volume will subsequently be facilitated by internal cell-transport through the vasculature without creation of open wounds. This therapeutic modality will thus give less post-treatment complications and less visible scarring compared to surgical procedures that are currently the only standard treatment for removal of cNFs in patients carrying the Neurofibromatosis Type 1 genetic condition.

The objective of the study is therefore to document that 20 MHz focused ultrasound is safe and effective in the treatment of NF1 associated cNF with high reduction of the measured volume of each treated tumor after 3 months, and with follow up registration of potential regrowth or development of new tumors in the treated and untreated regions at 6 and 9 months.

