6.2 Selection and grouping of tumors

Tumors to be included in the study will be selected and documented in the treatment session (visit 2) via collaboration between the participant and the treating physician. According to the willingness of the participant there may be 1-3 triplets of tumors representing all three categories (flat, sessile and globular) which would make a total of 3-9 cNF tumors treated and 3-7 cNF tumors biopsied per participant. The minimum number of cNF to be treated is three. The maximum number of cNF to be treated is 9. The minimum number of cNF to be biopsied is 3 and the maximum number of cNF to be biopsied is 7 to limit discomfort or inconvenience associated with healing. Ideally, paired sets of tumors representing all three categories (flat, sessile and globular) will be included. However, it is acknowledged that this may not be feasible to identify all three categories of tumors in pairs in each participant. It will be noted in the CRF which cNF is the control/reference and which are treated and sampled. The selected tumors will be documented by 2D and 3D photos.

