Scanning is non-invasive and not associated with any pain or discomfort. In this study the manual method of recording in vivo distances and thickness will be applied, and not the automatic facility having less accuracy (27). An example of an ultrasound imaging of a dermal tumor (not cNF) with qualitative measurement of the cross-sectional area is shown in Fig. 5.

[figure not shown]

Fig. 5. Example of measurement of a tumor cross-section using the Cortex DermaScan C device (not cNF). Source: https://cortex.dk/scientific-ultrasound-dermascan-c/

Ultrasound imaging assessment will be performed on all treated and control cNFs included in the evaluation at baseline (visit 2), one week after treatment (visit 3), 12 weeks after treatment (visit 4), 24 weeks/6 months (visit 5) and 39 weeks/9 months (visit 6). This will be done concurrent with 2D and 3D photos (Table 1).

6.3.2 6.3.2 Sweden – Biopsy

In Sweden, patients will undergo biopsy of a minimum of 3 cNFs (1 control/reference, 1 cNF biopsied one week after treatment, and 1 cNF at 12 weeks after treatment) and a maximum of 7 (1 control and 6 treated cNF) to characterize the baseline and treated response at two time points (1 and 12 weeks after treatment) (**Fig. 6**).

The control biopsy will be taken one week after the treatment (visit 3). Biopsies of the treated tumors will be taken one week after treatment (visit 3) and 3 months after treatment (visit 4). The pathologic analysis of these tumor samples will illustrate the short-term inflammatory response and mid-term healing effects respectively. If the patient is willing to have more tumors treated and biopsied, a maximum of 1 control biopsy and up to 6 biopsies from treated tumors per patient will be taken throughout the study. The schedule for biopsy characterization is illustrated in Fig. 6.

Tumors subject to biopsy are lost for clinical follow up, thus, up to nine lesions per patient will preferably be included in the study in the Swedish center. cNFs selected for biopsy must be 2-5 mm in diameter. Biopsy is preferably taken as a punch biopsy, but the investigator may decide to perform a surgical biopsy or a shave biopsy depending on participant's preference and the aim to possibly remove the entire lesion with the biopsy.

The tissue collected via biopsy will be assessed with standard histology and immunohistochemistry.

[figure not shown]

Fig 6. Schema for cutaneous neurofibroma biopsies.

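### Table 1 footnote 3 leaves open whether the 2-5 mm biopsy limit applies after treatment, so the 12-week histology may be selected on post-treatment size

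*Combined protocol and SAP*

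**What the plan says.** Table 1, footnote 3, states: "The biopsies will occur for cNF that are between 2-5 mm in size at visits 3 and 4". It goes on: "A minimum of one treated cNF will be biopsied at both visit 3 and visit 4". Section 6.3.2 gives the limit as "cNFs selected for biopsy must be 2-5 mm in diameter" and names no visit for the measurement. It allows, per Swedish patient, "a maximum of 7 (1 control and 6 treated cNF) to characterize the baseline and treated response at two time points", namely 1 and 12 weeks.

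Section 6.2 puts the choice of study tumours at visit 2. On sampling it says only: "It will be noted in the CRF which cNF is the control/reference and which are treated and sampled". It does not say when that entry is made, or how the sampled lesions are picked from the 3 to 9 treated.

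Section 5 sets as objective a "high reduction of the measured volume of each treated tumor after 3 months" but gives no figure for the expected reduction. Section 5.3 uses the one-week infiltrate to judge whether the whole lesion was treated and to guide later instrument settings. Section 6.3.2 gives the 12-week tissue a different role, mid-term healing.

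Baseline size is described in three ways: 2-5 mm for the five lesions needed at enrolment (Table 1, footnote 2), at least 2 mm with no ceiling (6.5.1), and 2-12 mm for a treated lesion (6.6).

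**The concern.** A size limit applied before treatment cannot depend on response. The same limit applied at visit 4 can, because post-treatment size is itself a measure of response. A Swedish investigator who takes footnote 3 literally, or who chooses among the treated lesions at visit 4, could pass over a lesion that has nearly gone and sample a larger one, since at least one treated biopsy is required at that visit.

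The 12-week tissue would then describe healing in lesions chosen partly by their outcome. Section 5.3.2 has histopathologists review the 3-month tissue of the first three patients to see whether the pathology is stationary. At the minimum of one treated biopsy each, that is 3 × 1 = 3 specimens, so the choice of lesion matters. Ultrasound depth measurement is planned in Denmark only, so biopsy is the Swedish centre's only planned view below the surface.

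**Working it through.** **1. The plan's own count.** One control plus two visits with 1 to 3 treated biopsies each (Table 1) gives 1 + 2×1 = 3 and 1 + 2×3 = 7. This reproduces the stated minimum and maximum. With 10 Swedish participants (6.5.6), visit 4 yields 10×1 = 10 to 10×3 = 30 treated specimens.

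**2. The texts side by side.**

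| Place | Size limit | When it applies |
|---|---|---|
| Table 1, footnote 3 | 2-5 mm | Visits 3 and 4 are named; they may qualify the size or only the timing of biopsy |
| 6.3.2 | 2-5 mm, for lesions selected for biopsy | No visit named |
| 6.2 | None stated | Study tumours chosen at visit 2; no time or rule for naming those to be biopsied |

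None of these says what happens if a lesion meant for biopsy is below 2 mm or no longer visible at visit 4.

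**3. When would a lesion leave the window?** Assume uniform shrinkage, so that volume scales with the cube of diameter. A lesion of baseline diameter d mm reaches 2 mm at a volume reduction of 1 − (2/d)³.

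| Baseline d (mm) | Calculation | Volume reduction |
|---|---|---|
| 2.0 | 1 − 1³ | 0% (any shrinkage) |
| 2.5 | 1 − 0.8³ | 49% |
| 3.0 | 1 − 0.667³ | 70% |
| 4.0 | 1 − 0.5³ | 88% (87.5%) |
| 5.0 | 1 − 0.4³ | 94% |

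**4. Direction and rough size.** The documents give no size distribution and no expected shrinkage, so this is illustration only. Baseline diameter was taken as uniform on 2-5 mm or on 2-12 mm. Volume reduction was drawn from a Beta(4m, 4(1−m)) distribution with mean m, independent of baseline size, with one million lesions per scenario. Eligible means 2-5 mm after treatment.

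| Mean reduction, all lesions | 2-5 mm start: below 2 mm | 2-5 mm start: mean reduction if eligible | 2-12 mm start: below 2 mm | 2-12 mm start: above 5 mm | 2-12 mm start: mean reduction if eligible |
|---|---|---|---|---|---|
| 0.30 | 10.6% | 0.28 | 3.2% | 62.1% | 0.33 |
| 0.50 | 22.9% | 0.45 | 7.0% | 52.8% | 0.54 |
| 0.70 | 45.0% | 0.60 | 15.5% | 36.8% | 0.74 |
| 0.90 | 81.0% | 0.72 | 48.3% | 12.2% | 0.88 |

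With 2-5 mm starts, the eligible lesions always understate the true mean reduction, and the gap widens as the treatment works better: 0.02 at a mean of 0.30, and 0.18 at 0.90. With 2-12 mm starts, the eligible lesions overstate it in the first three scenarios, because the ceiling bars large lesions that shrank little, and understate it slightly in the fourth. If the limit is applied to the baseline diameter, the eligible mean equals the true mean in every scenario.

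**5. Shape.** The limit is on diameter. If a lesion only flattens, so that height falls by 75% and diameter stays the same, volume falls by 75% and the lesion remains in the window. The thresholds in step 3 would then not apply.

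**The case against.** The strongest reply is that footnote 3 only says when biopsies occur. Elsewhere in that footnote, naming a visit gives the time of the biopsy. Footnote 2 uses the same 2-5 mm for enrolment, before treatment. Section 6.3.2 attaches the limit to lesions selected for biopsy, and 6.2 puts the selection of study tumours at visit 2. A limit at visit 4 would also sit badly with the required treated biopsy there: if every lesion shrank strongly, none might qualify. Section 6.6 expects histology after 3 months to be able to document incomplete cure, which fits poorly with a rule that leaves out cleared lesions. Fig. 6, the biopsy schema, is not shown in the text available for this review and might settle the matter.

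Much of this stands. The timing-only reading is reasonable and may be what is intended. It does not close the gap, because 6.2 fixes only which tumours enter the study. No section says when the lesions for biopsy are named, how they are chosen, or at which visit 2-5 mm is measured.

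A reader might go further and infer that a lesion below 2 mm cannot be sampled, that an unshrunken one is taken in its place, and that the histology sees mainly poor responders. The documents do not support this. No section bars a lesion under 2 mm or provides for substitution, and the direction of any bias depends on baseline sizes that the plan describes inconsistently. Nor does the point reach lesion coverage or device settings, which 5.3 ties to the one-week tissue.

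**Conclusion.** The point holds as a risk of selecting on outcome. It does not show that a biased rule is certainly in force. The wording permits a post-treatment size check, and nothing in the plan prevents the biopsy lesions from being picked at visit 4. In either case the 12-week histology depends on post-treatment size.

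Good responders are under-represented if lesions start at 2-5 mm and shrink uniformly; both are assumptions. In the illustration at a mean reduction of 0.70, 45% of such lesions fall below 2 mm and the eligible lesions average 0.60. With larger lesions the direction can reverse, and with pure flattening the effect may vanish. The size is therefore uncertain, and its sign cannot be fixed from the documents.

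Histology is exploratory and confined to one centre with a target of 10 participants. The primary endpoint, the sample size and the one-week questions are unaffected. The text should be changed before biopsies start, because the change is cheap and removes the risk under either reading, but the point does not threaten the trial's main conclusion.

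**What to change.** - In footnote 3 and in 6.3.2, state that 2-5 mm is the baseline diameter, measured at visit 2.
- In 6.2, require the CRF to record, before treatment, which lesions are assigned to biopsy at visit 3 and which at visit 4.
- State that assigned lesions are not selected or replaced according to their size after treatment.
- Report beside each histology result the size at biopsy, or that no lesion was visible or no sample was taken.
- Reconcile the baseline size statements in Table 1 footnote 2, 6.5.1 and 6.6, so that a reader can tell which lesions the biopsy limit leaves out.

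The cost is a few sentences and one CRF entry made at visit 2, where lesions are already documented by 2D and 3D photographs. No extra biopsies are needed. The small downside is that some assigned sites will show little visible lesion and must be located from the baseline photographs.

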1.1 Summary of the clinical investigation

The overall objective of this study is to evaluate the safety, tolerability, and efficacy of cutaneous neurofibromas (cNF) removal in adults with Neurofibromatosis Type 1 (NF1) using high-intensity focused ultrasound (HIFU).

With an incidence of 1/2500 to 1/3500, Neurofibromatosis Type I (NF1) is among the most common single-gene inherited conditions worldwide (1, 2). The genetic condition predisposes to multiple forms of histologically benign and malignant neoplasms. The most common tumor across all people with NF1 is cutaneous neurofibroma (cNF), impacting up to 99% of adults (3-7). These tumors can number in the hundreds to thousands on a given individual, most often appear between late school age and in the second decade, and increase in number and size across the lifespan (3-5, 8-12).

In many patients, cNF are socially debilitating, painful and impede activities of daily living (4, 5, 10-14). Multiple different appearances of cNF exist as reported from patients and clinicians. These can range from barely visible flat nodules with subtle discoloration, to large and pedunculated masses. One proposed classification system to describe the clinical appearance of cNF assigns one of five subcategories: nascent, flat, sessile, globular, or pedunculated (15). Nascent lesions (very small dispersed tumors) and peduncular neurofibromas (protruding tumors with a narrow base) are not subject to study as they are not logic candidates for HIFU treatment at this early stage. The typical appearance of the cNF-categories relevant for treatment in this study is illustrated in Fig. 1.

Despite the remarkable prevalence of cNFs in people with NF1 and their documented influence on quality of life (QoL), current treatment is limited to surgical removal or the use of various devices that cause tissue destruction showing mixed, but largely low-efficacy success, to date (11, 16-18).

While blade-based surgical removal allows complete removal of the lesion(s), this method is impractical to address the many tumors affecting a typical adult with NF1, thus forcing patients to select specific tumors to remove. Additional drawbacks of surgical resection include variable scarring, and the time required for the procedure and healing. Alternative approaches that enable the removal of larger numbers of lesions per session include electrosurgical ablation, laser-based treatments, and radiofrequency ablation all reported to have variable outcomes(11, 15-17, 19-22).

[figure not shown]

Fig. 1. Three subtypes of cutaneous neurofibromas considered for the current study.

The investigational device used in this study is a Danish developed system. As the first of its kind in the world, it is capable of controlled and targeted thermo-mechanical treatment to small intradermal volumes containing neoplastic cells, without inflicting damage to the surrounding tissue (23-26).

The device is proposed to be used in a non-ablative modality, where treatment does not damage the skin's basement membrane, and the skin surface thereby remain intact. Healing after treatment will thus be facilitated by internal cell transport through the vasculature, and risks of post-treatment complications or visible scarring will be minimized (23-25, 27).

The current protocol presents an investigation with an evaluation of the safety and efficacy profile 3 months after a single 3-5 minute treatment. Subsequent follow-up of secondary endpoints is done every third month until the end of the study 9 months after the treatment. The activities of the investigation are summarized in Table 1, and a graphic presentation of the patient-flow and actions are given in Fig. 2.

Provided that the expected positive clinical results can be verified, this new method could have potential for widespread use as an important replacement or compliment to existing methods for treatment of cNF.

RECRUITMENT (Pre-study)	NF1 Patients with Cutaneous Neurofibro	
ACCEPTANCE & REGISTRATION (Visit 1)	cNFs for treatmen (Inclusion Criteria) min. 5 pcs	t Exit (Exclusion Criteria)
TREATMENT (Visit 2)	Photo / US (DK) HIFU min. 3 pcs 2 + Photo / US (DK)	Control
WEEK 1 (Visit 3)	Photo US (DK)	^{2 pcs} Photo US (DK)
MONTH 3 (Visit 4)	min. 2 pcs Photo US (DK)	1 pcs Photo US (DK)
MONTH 6 (Visit 5)	Photo US (DK)	1 pcs Photo US (DK)
MONTH 9 (Visit 6)	min. 1 pcs Photo US (DK)	1 pcs Photo US (DK)
EVALUATION (Study objective)	Final Report	atory process?

Fig. 2. Study flow chart. The study is an initial tolerance-study with the objective to investigate if a new therapeutic modality is safe, efficient and feasible, and thereby should be investigated further in larger future studies. cNF to be treated can be anywhere on the body with the exception of face, shoulders and the breast.

2 Identification and description of the investigational device

2.1 System ONE-M

The investigational device, called TOOsonix System ONE-M, is described in detail in the investigator's brochure, which includes details on model, type, software, accessories, the manufacturer, and the regulatory status of the device authorized for clinical studies on humans. The device is shown in Fig. 3.

Fig. 3. TOOsonix System ONE-M; 20 MHz focused ultrasound applied to skin with a selection of handpieces (depth of focal point in the skin 0.8, 1,3, 1,8 and 2,3 mm). Treatment is surveyed with a camera incorporated in the handpiece.

The operating principle of focused ultrasound has been used for decades for non-invasive treatment of lesions in internal organs (28-33). Acoustic energy is generated in a transducer with a concave geometry allowing the emitted sound to concentrate in a high-energy focal zone inside the body, where a thermal lesion can be positioned in the target of interest chosen to be treated.

Depending on instrument construction and setting, short pulses can produce a controlled thermal insult in the target. This target could be; e.g. a kidney stone or a cancer as exemplified by a breast cancer, thyroid cancer or a prostatic carcinoma resulting in thermal necrosis and destruction of the target. Focused ultrasound can also be used for treatment of intracranial targets, such as centers responsible for essential tremor and Parkinson's disease (26, 31, 34). The HIFU operating principle, which illustrates the application to skin, is shown in Fig. 4.

The convergent ultrasound beam, on its passage through tissues to reach the focal point, with proper settings, will not exert damage to the passage medium of tissue between transducer and target. Thus, the necrotizing or ablating effect can be set to match a desired level in the skin without causing effects in the adjacent tissue above, below and around.

Focused ultrasound devices, including the device under study, are designed to produce a focal heating in a focal point reaching up to 65 °C. This is a level that is high enough to produce cellular death in the focal zone, but low enough not to transmit major caloric energy to the surrounding tissue (23, 24).

[figure not shown]

Fig. 4. Schematic illustration of the HIFU principle with concentration of the ultrasound energy inside the skin in a focal point exposed to a thermal insult causing cell death.

Treatment of internal organs with focused ultrasound has been documented in clinical research, and the method is now used around the world in oncology clinics of excellence (26). Treatment of internal targets in the body requires deep penetration and therefore need to operate with longer wavelengths at lower frequencies (from 500 kHz to 5 MHz), where attenuation of ultrasound is relatively low. For the treatment of dermal lesions, much smaller wavelengths at higher frequencies (> 15 - 20 MHz) is however needed, since targets, such as skin tumors, have small dimensions and need selective treatment with a small and well-controlled focal point both vertically and horizontally (23).

As the TOOsonix device is the first device operating at 20 MHz, the resolution allows for selective treatment of small sized targets in the skin. The device has shown efficacy in other diseases limited to the skin in which the goal was to eradicate the neoplasm without damaging the epidermis. There is therefore potential that the TOOsonix device can address multiple sizes and forms of cNF without the burden of scarring.

Practical operation of the investigational device is comparable to conventional dermatological lasers, which are covered in the formal specialist courses dermatologists must pass. An introductory training in focused ultrasound is needed, with practical training performed on some suitable tissue-like objects. TOOsonix A/S is offering introductory information, theoretically and practically, at the start of study, including instruction in the use of different hand pieces with different penetration depths.

During operation, a treatment dose of typically 150 milliseconds duration is applied to the skin under real-time supervision using the integrated camera showing a magnified image of the skin surface. Repeated ultrasound dosing is administered in close proximity to each other and positioned to cover the entire skin lesion in a "shoulder-by-shoulder" pattern. At the time of a dose-activation, a circular shockwave-effect on the outer skin is displayed, and it can be monitored and adjusted such that an applied dose is not too weak and not too strong.

Depending on the choice of hand piece (focal depth) used on the investigational device, the treatment can be selected to be ablative, with transport of dead cells into a superficial wound crust through a damaged basement membrane, or non-ablative with internal transport of dead cells through the body's vasculature.

The device will be applied to cNFs that are intradermal. Visible cNFs commonly vary in diameter from 1 mm up to 1 cm in size. cNFs are, irrespective of size, typically covered by a roughly 150 µm

thick epidermis and 200-500 μ m thick rim of dermis. Neurofibromas are by histology composed of Schwann cells, and are variable connective tissue components in a loose and poorly defined structure.

The treatment in this study is thus aimed at use in the non-ablative modality, where cell death in the dermis is created without damaging the basement membrane, subsequently minimizing the risk of broad tissue damage to dermal collagen, and thereby reducing unintended scar formation after healing.

To obtain the non-ablative treatment modality, hand pieces with nominal focal depth (NFD) depth of 1.8 mm or 2.3 mm will likely be the preferred standard in this study, while allowing for discretion of the investigator to use any available hand piece deemed appropriate based on the pre-treatment assessment of the thickness and invasion level of the tumor in the skin. Two more superficial hand pieces with NFD of 0.8 mm and 1.3 mm are available with the standard device accessories from the manufacturer.

The device displays the instrument settings and the number of shots applied during a treatment course, thereby relieving the operator of extraneous distractions. Additionally, the device works by ultrasound as the sole modality, relieving the patient the undue burden of additional medicines, electromagnetic radiation, or other more invasive measures.

3 Justification of the design of the clinical investigation

In this study, the TOOsonix System ONE-M is applied to cutaneous neurofibromas (cNF) consistent with neurofibromatosis type I (NF1).

Given the very low number of available dermatologic agents for the treatment of cNF, and the lack of data about the specific performance of these instruments and formal clinical assessment, this study will systematically assess the TOOsonix device for tolerability, biologic effect and efficacy as assessed by patient reported outcome and image assessment before and after treatment. This data will help determine if additional study of the TOOsonix device is warranted for cNF in people with NF1.

The investigational device is a Danish developed system aimed specifically at high frequency operation (20 MHz). At this high frequency, the device, as the first of its kind, allows controlled and targeted treatment of small intradermal volumes, thus with limited damage to the surrounding tissue.

The investigational device has passed pre-clinical studies in experimental laboratory models and in a safety study on Göttingen minipigs as reported in the IB and published in the literature (23, 24).

The pre-clinical experiments showed the following key results and conclusions:

- The 20 MHz ultrasound output is a well-defined ultrasound cone with a sharp focal point as demonstrated in laboratory measurements and in tissue-mimicking phantom gel simulating skin.
- The produced thermal lesion is highly reproducible from dose to dose.
- The depth of the focal point can be chosen and positioned as intended depending on the selected hand piece.
- The temperature in the focal point reproducibly matches 65 °C.

- The extension/severity of the heat effect in a phantom and read as necrotizing effect and heat lesion in the pig study was tunable within the range of available instrument settings, and reproducible.
- Depending on device setting, non-ablation subclinical effects can be induced, alternatively ablation/necrotizing effects, the former being relevant for cNF therapy.
- Post-treatment wound and healing studied in the pig followed over time (12 weeks) depended on the applied ultrasound energy.
- Isolated single dosing had much lower, or no, necrotizing effects as compared to multiple shoulder-by-shoulder dosing applied to a larger field.
- Histology after three months indicated mild fibrosis in pigs treated with higher ultrasound energy, however, clinical scar formation was not visible, or only barely visible.
- Studies indicated the depth of the ultrasound lesion in the dermis are well controlled by way of proper selection of instrument settings, and the choice of hand piece.
- Depending on dose, a transient wheal and flare reaction, with redness and edematous swelling, occurred within minutes and faded within about 30 min. This reaction is comparable to skin reactions from dermatological lasers. The reaction is considered to be caused by traumatic histamine release.
- Ultrasound treatment in clinical use may be associated with instant pain and possibly itch.
- Studies indicated no unexpected adverse events, and no systemic safety concerns.

The skin lesions observed in the pig models and human treatments therefore justifies the present protocol addressing treatment of human cNF, which are superficial skin lesions of small size, and easy to cover with visually guided shoulder-by-shoulder applied ultrasound shots.

This study is the original and the first systematic study of 20 MHz focused ultrasound applied to NF1 associated cutaneous neurofibromas. The method has the potential to open a new venue of clinically useful tumor mitigation therapy in people with NF1 where there is a major unmet need.

4 Benefits and risks of the investigational device, clinical procedure, and clinical investigation

The anticipated benefit of the 20 MHz HIFU modality in treatment of benign neurofibromas is to develop and confirm a new targeted therapy with a high benefit-risk ratio compared to existing surgical methods.

Cutaneous NFs for treatment will be selected in agreement with patients. Visible skin areas will be avoided since scar-formation resulting from HIFU treatment of cNF is not yet documented. Specifically, lesions on the face, shoulders and breasts will not be treated as these areas are especially vulnerable to development of scaring.

Participants shall be informed about potential risks and discomforts of the HIFU treatment before the treatment is applied. Persons having psychological or neurologic risk of pain are not included in the study. Persons with any acute or chronic medical condition, which in the opinion of the investigator, could interfere with this study are also not included in the study.

At the Danish center, the study will include ultrasound imaging assessment before and after HIFU treatment. This method is non-invasive and known to be without risks to the patients.

At the Swedish center, the study includes a minimum of 3 and a maximum 7 small punch biopsies taken from control and treated lesions during the study. Topical anesthesia will be used according

to normal routine before biopsy. Biopsies taken on cNFs are part of the routine treatment regime, and the overall risk is known to be minor and serious adverse events are very unlikely.

Focused ultrasound applied as short doses producing 65 °C heat in a cancer is widely documented in the literature as having a necrotizing effect on internal cancer tissue followed by clinical healing or cancer reduction (28-34). It is expected that the HIFU lesions in skin are equally sensitive to ultrasound generated heat.

The expectation regarding treatment of skin is therefore high, since these tumors are small and superficial, and therefore visible and easy to diagnose and target. The treatment effect can be dosed precisely under real-time visual supervision from the investigational device.

Anticipated local adverse effects are immediate wheal and flare reactions at the treatment site, and complications of wound healing, including the potential risk of bacterial infection and scarring. The former is significantly reduced when treatment is administered in the proposed non-ablative modality, where the skin barrier remains intact, and bacterial access thereby remains closed. Risk of scarring after healing of insults to the lower half of the dermis is known, but also depends on anatomical site and constitutional factors (24). Compared to potential scarring from healing of open surgical wounds the visual result is however considered to be very beneficial.

The treatment carries very low potential risk of systemic adverse effects except for pain on treatment due to heating in the treatment zone. Pain has an instant onset, but is very short, since the preferred pulse duration is only 150 milliseconds. However, participants shall be instructed about pain of treatment before treatment is provided.

Histamine release in the treated area may cause wheal-and-flare associated with itch on the treated site, however, traumatic wheals are short-lived and fade over 20-30 min (24). HIFU is, in comparison to light, not expected to interfere with the effect or metabolism of circulating drugs.

Finally, HIFU is a physical acoustic wave that can be transmitted through coupled media only. Unlike in laser treatments, users or patients are therefore not at risk of any unintentional exposure. The treatment can thus be conducted in a normal clinic setting without use of eye-protection PPE etc.

The results of this research may gain further understanding of use of these treatments in providing a new tool for treating cNF and potentially helping prevent growth of such lesions. There may or may not be direct benefits to participants in this study, however previous trials showed improvement in lesion appearance/clearance, as well as high patient satisfaction.

5 Objectives and hypothesis of the clinical investigation

The hypothesis of this study is, that small and highly localized acoustic focal zones produced by a new HIFU device non-invasively can induce acute cell-death in cutaneous neurofibromas (cNF) without disrupting the skin's basement membrane. The healing of the treated volume will subsequently be facilitated by internal cell-transport through the vasculature without creation of open wounds. This therapeutic modality will thus give less post-treatment complications and less visible scarring compared to surgical procedures that are currently the only standard treatment for removal of cNFs in patients carrying the Neurofibromatosis Type 1 genetic condition.

The objective of the study is therefore to document that 20 MHz focused ultrasound is safe and effective in the treatment of NF1 associated cNF with high reduction of the measured volume of each treated tumor after 3 months, and with follow up registration of potential regrowth or development of new tumors in the treated and untreated regions at 6 and 9 months.

